### 11.5.1.4. Adverse Event Reporting Period

The adverse event reporting period for this trial begins upon signing of informed consent and ends 28 days after the last study treatment administration.

However, if a patient begins a new anticancer therapy earlier than 28 days after the last dose of study treatment administration, the adverse event reporting period will end at the time the new anticancer therapy starts.

All the adverse events that occur in trial patients during the adverse event reporting period must be reported to the Sponsor, whether or not the event is considered related to the study treatment.

### 11.5.1.5. Adverse Event Follow Up after the End of the Reporting Period

The following events should be followed after the end of the reporting period (i.e., 28 days after the last study treatment administration):

1. SAEs with outcome ‘not recovered’ or ‘unknown’ at the end of the reporting period.
2. Non-serious events classified as related to the investigational study treatment with outcome ‘not recovered’ or ‘unknown’ at the end of the reporting period.

These events should be followed until they resolve or until the Investigator determines, whenever possible, that they have become “chronic” or “stable”. Resolution of such events is to be documented on the SAE Form and/or on eCRF.

In addition, if after the end of the reporting period, suspected serious adverse reactions or deaths are reported to the Investigator and he/she believes that they are related to the IMP, it is the Investigator’s responsibility to report these suspected serious adverse reactions to the Sponsor. Such suspected serious adverse reactions will be reported using a Serious Adverse Event Report or by any other way chosen by the Investigator.

#### 11.5.1.6. Relationship to the Investigational Medicinal Product

The relationship of the adverse event will be assessed by means of the question “Is there a reasonable possibility that the event may have been caused by the study drug?” The Investigator should respond to this question with either ‘Yes’ or ‘No’.

‘No’ equals to Unrelated/Unlikely, i.e. there is no reasonable possibility that the study drug caused the event; Yes equals to = Related, i.e. there is a reasonable possibility that the study drug caused the event.

#### 11.5.1.7. Reporting Requirements

Each adverse event has to be classified by the Investigator as SERIOUS or NON-SERIOUS (as per paragraph 11.5.1.1.2). This classification of the event determines the reporting procedures to be followed. If a serious adverse event occurs, reporting will follow local and international regulations, as appropriate.

If a serious adverse event occurs the Sponsor Pharmacovigilance has to be notified within 24 hours of awareness of the event by the Investigator, by e-mail (here below Pharmacovigilance address/contacts). Further detailed reporting procedures are described in the Study Manual.

PPD

The initial report should be followed by submission of more detailed adverse event information as soon as it is available. Additional follow-up should be provided up to the resolution of the SAE, the Investigator determines it has become chronic or stable (not recovered) or a new anticancer therapy is initiated.

Reporting requirements for adverse events are summarized in the following table.

REPORTING REQUIREMENTS FOR ADVERSE EVENTS		
Seriousness	Reporting Time	Type of Report
SERIOUS	Within 24 hours	Initial report on designated SAE form
	As soon as available	Follow-up/Final report on designated SAE form
NON-SERIOUS	As per eCRF procedure	Appropriate section of eCRF

Suspected Unexpected Serious Adverse Reactions (SUSARs) will be reported by Sponsor or designee to all competent Regulatory Authorities, to the Ethics Committees and to all the Investigators involved, according to local regulations and requirements stated in ICH Good Clinical Practice.

In the rare event that the Investigator does not become aware of the occurrence of a serious adverse event immediately (for example, if an outpatient trial patient initially seeks treatment elsewhere), the Investigator has to report the event within 24 hours after learning of it and document his/her first awareness of the adverse event.

Serious adverse events should also be consistently recorded in the appropriate section of eCRF.

Non-serious adverse events have to be reported in the appropriate section of eCRFs only excluding Adverse Events of Special Interest (see section 11.5.1.1.3).

#### 11.5.1.8. Recording Adverse Events in the Case Report Forms

Information on AEs must be evaluated by a physician and recorded in source documents such as the hospital file. AEs have to be reported in the eCRF as aforementioned. The Investigator will also be asked to assess the relationship between the AE and the investigational medication.

- Preexisting Conditions

In this study, a preexisting condition (ie, a disorder present before the AE reporting period started and recorded in the medical history) should not be reported as AE unless the condition worsens or episodes increase in frequency during the AE reporting period.

All relevant symptoms, occurring after the ICF signature and before the first drug intake, should be reported (with CTC grade) in the baseline AE page, including disease-related symptoms (e.g. fatigue, bone pain, etc). Abnormal lab values do not need to be reported as AE if related to the disease (e.g. anemia, thrombocytopenia), or a medical condition already reported in Medical History (e.g. hyperglycemia for a patient with diabetes).

- Procedures

Diagnostic and therapeutic non-invasive and invasive procedures, such as surgery, should not be reported as AE. However, the medical condition for which the procedure was performed should be reported if it meets the definition of AE. For example, an acute appendicitis that begins during the AE reporting period should be reported as AE and the resulting appendectomy should be recorded in the source documents.

- Symptoms of the Disease

All relevant symptoms present before the AE reporting period started, have to be recorded in medical history. During treatment, the specific symptoms of the disease have to be reported as adverse events if they match with new occurrence or worsening in severity or in frequency versus the baseline visit. Note: the general wording “Progression of the disease” should not be reported as adverse event.

- **Abnormal Laboratory Findings**

Abnormal laboratory findings occurring during the AE reporting period have to be recorded as adverse events when they cause treatment change (dose omission/reduction/delay/discontinuation) or when require clinical intervention (e.g., hospitalization for further investigation or management of the laboratory abnormality). Disease-related anemia and/or thrombocytopenia requiring transfusion support should not be reported as AE if management of the event(s), e.g. transfusion need, has not changed since ICF signature, but they should be reported as AE if the event(s) results in dose omission/delay/discontinuation/reduction, or in case the event worsens requiring hospitalization (not previously needed) or more frequent transfusions. Note: uncomplicated and asymptomatic abnormal laboratory findings have not to be reported as adverse events. The corresponding values have to be reported only in the relevant eCRF sections (e.g., hematology, biochemistry).

- **Abnormal Findings in vital signs, physical exams and/or ECG**

Abnormal findings in vital signs, physical exam and/or ECG, have to be reported as adverse events if they are clinically significant new events or events worsening as compared to baseline. Clinical significance is defined as any variation, which has medical relevance based on at least one of the following criteria:

- Induces relevant clinical signs or symptoms;
- Requires active intervention;
- Requires change of study medication (dose omission / reduction / delay / discontinuation);
- The abnormality or investigational value is clinically significant in the opinion of the investigator.

#### **11.5.1.9. Grading of Adverse Event Severity**

In this study the severity/intensity of AEs will be graded using the Common Terminology Criteria for Adverse Events (CTCAE, Version 5.0) of the US National Cancer Institute (see website: [https://ctep.cancer.gov/protocolDevelopment/electronic\\_applications/docs/CTCAE\\_v5\\_Quick\\_Reference\\_8.5x11.pdf](https://ctep.cancer.gov/protocolDevelopment/electronic_applications/docs/CTCAE_v5_Quick_Reference_8.5x11.pdf))

For each event, each change in severity grade should be reported. If an event swings repeatedly back and forth from a grade to another, it is possible to record it as <intermittent AE>.

For adverse events not reported in the CTCAE Version 5.0, the Investigator will use the Grade or adjectives reported in [Table 4](#).

**Table 4. Grading of Adverse Event Severity  
for Events not reported in the CTCAE Version 5.0**

Grade	Adjective	Description
Grade 1	Mild	Does not interfere with patient's usual function
Grade 2	Moderate	Interferes to some extent with patient's usual function
Grade 3	Severe	Interferes significantly with patient's usual function
Grade 4	Life-threatening	Results in threatening to life or in an incapacitating disability
Grade 5	Death	Death related to AE

Note the distinction between the term “serious” and “severe”, which are not synonymous. The term “severe” is used to describe the intensity of a specific event (i.e., severe headache) while the term “serious” is based on patient/event outcome or action criteria. Seriousness (not severity) serves as a guide for defining regulatory reporting obligations. For example, vomiting Grade 1 for which a hospitalization occurred is a serious event even if the event is not severe.

#### 11.5.1.10. Exposure In Utero

If a female patient becomes or is found to be pregnant while receiving the study drug or within 208 days from its discontinuation, the Investigator should transmit this information using the Part I of Exposure in Utero (EIU) Form to Sponsor Pharmacovigilance. This must be done irrespective of whether an adverse event has occurred and within 24 hours of awareness of the pregnancy. However, if the patient begins a new anticancer therapy before 208 days after the last dose of study treatment administration, the exposure “in utero” reporting period will end at the time the new treatment is started.

The Investigator will follow the patient until completion of the pregnancy or until pregnancy termination (i.e., induced abortion) and then notify the Sponsor Pharmacovigilance of the outcome within 5 days or as specified below. The Investigator will provide this information completing Part II of EIU form. The reason(s) for an induced abortion must be specified.

If the outcome of the pregnancy meets the criteria for immediate classification as a serious adverse event (i.e., spontaneous abortion, stillbirth, neonatal death, or congenital anomaly [including that in an aborted fetus]), the Investigator should follow the procedures for reporting serious adverse events, i.e., report the event to the Sponsor (as described in Section 11.5.1.7)

In the case of a live birth, the “normality” of the newborn must be assessed at the time of birth and for a minimum follow-up of at least three months.

The “normality” of an aborted fetus can be assessed by gross visual inspection unless pre-abortion laboratory findings are suggestive of a congenital anomaly.

Other pregnancy outcomes that are classified as SAEs:

- “Spontaneous abortion” includes miscarriage and missed abortion.
- All neonatal deaths that occur within 1 month of birth should be reported, without regard to causality. In addition, any infant death after 1 month that the Investigator assesses as possibly related to the “in utero” exposure to the study drug should also be reported.

If a female partner of a male patient taking the IMP becomes pregnant while the male patient is still on IMP or within 118 days after last dose of IMP, the male patient taking IMP should notify the Investigator, and the pregnant female partner should be advised to call her healthcare provider immediately. If a pregnancy related event is reported in a female partner of a male patient, the Investigator should ask if the female partner is willing to share information with the Sponsor Pharmacovigilance and allow the pregnancy related event to be followed up to completion.

The Investigator has to submit the information of pregnancy or suspect pregnancy of a female partner of a male patient to the Sponsor Pharmacovigilance, by e-mail, using the EIU Form, within 24 hours from his/her awareness of the event.

#### 11.5.2. Laboratory Safety Assessments

Laboratory safety assessments will include repeated evaluation of hematology, biochemistry and coagulation parameters, urinalyses and pregnancy test, according to timing reported in Section 1, Schedule of Events (Table and related footnotes). Investigators may order additional blood tests for planning treatment administration, dose modification, or further evaluation of adverse events.

The following laboratory parameters will be used to monitor safety:

CCI

NMS-03592088  
Protocol for Study MKIA-088-001

MKIA-088-001\_P9  
Version 9\_28 February 2024

CCI  
[Redacted text block]

[Redacted text block]

[Redacted text block]

[Redacted text block]

[Redacted text block]

[Redacted text block]

NMS-03592088  
Protocol for Study MKIA-088-001

MKIA-088-001\_P9  
Version 9\_28 February 2024

CCI

NMS-03592088  
Protocol for Study MKIA-088-001

MKIA-088-001\_P9  
Version 9\_28 February 2024

CCI

NMS-03592088  
Protocol for Study MKIA-088-001

MKIA-088-001\_P9  
Version 9\_28 February 2024

CCI

## 11.6. Other Assessments

### 11.6.1. Pharmacokinetic Assessments

#### 11.6.1.1. Blood Sampling in Phase I

CCI

[figure not shown]

NMS-03592088  
Protocol for Study MKIA-088-001

MKIA-088-001\_P9  
Version 9\_28 February 2024

**Table 5. PK Blood Sample Collection for Schedule A (Phase I: Dose Escalation)**

CCI

A large black rectangular box redacting the content of Table 5.

**Table 6. PK Blood Sample Collection for Schedule A (Phase I: Dose Expansion)**

CCI

[figure not shown]
A large black rectangular box redacting the content of Table 6.

NMS-03592088  
Protocol for Study MKIA-088-001

MKIA-088-001\_P9  
Version 9\_28 February 2024

**Table 7. PK Blood Sample Collection for Schedule B (Phase I: Dose Escalation)**

CCI

[figure not shown]

NMS-03592088  
Protocol for Study MKIA-088-001

MKIA-088-001\_P9  
Version 9\_28 February 2024

**Table 8. PK Blood Sample Collection in the backfill cohorts (Phase I)**

CCI

[figure not shown]

NMS-03592088  
Protocol for Study MKIA-088-001

MKIA-088-001\_P9  
Version 9\_28 February 2024

**Table 9. PK Blood Sample Collection in the backfill cohort for food effect investigation**

CCI

NMS-03592088  
Protocol for Study MKIA-088-001

MKIA-088-001\_P9  
Version 9\_28 February 2024

CCI

[Redacted]

[Redacted]

[Redacted]

[Redacted]

[Redacted]

[Redacted]

[Redacted]

[Redacted]

[Redacted]

[Redacted]

**Table 10. PK Blood Sample Collection Schema (Phase II -all patients)**

CCI

[Redacted Table Content]

Details on PK samples collection, processing, storage and shipping instructions are provided in the Study Manual. Timing of sampling may be modified based upon emerging PK data from the dose escalation part of the study. Analysis will be performed at the central facility delegated by the Sponsor.

#### 11.6.1.3. Urine Sampling

CCI

[REDACTED]

[REDACTED]

[REDACTED]

[REDACTED]

[REDACTED]

[REDACTED]

[REDACTED]

#### 11.6.1.4. Bioanalytical method in plasma and urine

CCI

[REDACTED]

## 11.6.2. Translational Research

### 11.6.2.1. DNA extraction for genomic analysis

CCI [REDACTED]  
[REDACTED]  
[REDACTED]  
[REDACTED]  
[REDACTED]  
[REDACTED]  
[REDACTED]

### 11.6.2.2. NGS Analysis of FLT3 and other selected genes

CCI [REDACTED]  
[REDACTED]  
[REDACTED]  
[REDACTED]  
[REDACTED]  
[REDACTED]  
[REDACTED]

### 11.6.3. Biomarker assessment

CCI [REDACTED]  
[REDACTED]  
[REDACTED]  
[REDACTED]

#### 11.6.3.1. PIA analysis for FLT3 pathway

CCI [REDACTED]  
[REDACTED]  
[REDACTED]  
[REDACTED]

[REDACTED]  
[REDACTED]  
[REDACTED]  
[REDACTED]  
[REDACTED]  
[REDACTED]  
[REDACTED]  
[REDACTED]  
[REDACTED]  
[REDACTED]

NMS-03592088  
Protocol for Study MKIA-088-001

MKIA-088-001\_P9  
Version 9\_28 February 2024

### 11.6.3.2. Circulating CSF1 analysis

CCI [REDACTED]  
[REDACTED]  
[REDACTED]

## 12.2. Definition of Analyzed Study Populations

For the purpose of the analysis, the following patient populations are defined and the endpoints, to be analyzed in these populations, are specified:

- *Enrolled Patients*: This population will include all patients who are enrolled in the clinical study, regardless of whether patients receive treatment or not. This population will be evaluated in the analysis of patients' disposition.
- *Treated Patients*: The treated patient population consists of all enrolled patients who actually receive at least one treatment administration. This population will be evaluated in the analysis of patient disposition, baseline characteristics, treatment exposure, efficacy and safety.
- *Patients evaluable for determination of DLT (by dose schedule and dose level)*: for each schedule and dose level tested, this population includes all patients enrolled in dose escalation part who receive at least 70% of drug in the first cycle, unless the reason for non compliance is drug-related toxicity, and for whom a DLT assessment is available within the DLT window. In case the patient does not fulfill one or more of the aforementioned criteria, he/she will be replaced.
- *Patients evaluable for efficacy analysis (efficacy dataset)*: This is the patient population which consists of all enrolled patients in the Phase II part who are treated at the RP2D, have  $\geq 1$  on-treatment hematologic assessment(s) (i.e. they must have adequate bone marrow response evaluation). Patients who experience early death or withdrew prior to response assessment, or had technically suboptimal bone marrow sample precluding assessment, are non-evaluable for response and are excluded from the efficacy dataset. For cohort 1 and 2, only the subset of patients with FLT3-ITD mutation and no D835 and I836 mutations based on the central test will be included in this population.
- *Patients evaluable for PK analysis*: treated patients will be considered evaluable if they have sufficient baseline and on-study sampled material to provide interpretable results.

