3.2. Endpoints

3.2.1. Primary Endpoint

Phase I:

- Drug related first-cycle dose limiting toxicities (DLTs).

Phase II :

- FLT3-ITD mut AML: Composite Complete Remission (CRc) Rate, i.e., Complete Remission (CR) + Complete Remission with Incomplete Hematologic Recovery (CRi), as defined by the Investigators based on the 2022 European LeukemiaNet (ELN) recommendations [2]
 - Composite Complete Remission Rate (CRc) = CR + CRi

Statistical Analysis Plan

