For Europe countries, up to 4 backfill cohorts of up to 10 patients each may enroll at doses and schedules no higher than RP2D or exposure equivalent and may include the following: 1) first cycle at reduced dose/exposure relative to RP2D to collect additional PK, matched PK/ECG for standard E14 update exposure/QTc, biomarkers, and anti-cancer activity followed by subsequent cycle up to RP2D or exposure equivalent; 2) food effect with first cycle no higher than RP2D or exposure equivalent followed by subsequent cycle with standard meal on day 1 of cycle 2 only. After day 1 of cycle 2, patients will continue treatment in fasting condition.

In Phase II, the following cohorts will be studied in parallel:

Cohort 1 (40 patients with a futility analysis at 10 patients): patients with AML FLT3 Internal Tandem Duplication (ITD) mutation as assessed by central laboratory, who have failed standard of care including venetoclax and gilteritinib based therapies. Dose and schedule will be within the defined exposure cap rule defined above. The enrollment in this cohort may be restricted to patients with specific prior lines/therapies and/or mutations, based on Sponsor decision.

Cohort 2 (40 patients with a futility analysis at 10 patients): patients with AML FLT3 Internal Tandem Duplication (ITD) mutation as assessed by central laboratory, who have failed standard of care. Dose and schedule will be within the defined exposure cap rule defined above. The cohort may be restricted to patients with specific prior lines/therapies and/or mutations, based on Sponsor decision.

The Sponsor will control the patient assignment to cohorts and may terminate any cohort in any phase at any time during the study based on safety, PK or strategic reasons.

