7. ANALYSIS POPULATIONS

As stated in the CT Protocol, for the purpose of the analysis, the following patient populations are defined: Enrolled Patients, Treated Patients, Patients evaluable for determination of DLT (by dose schedule and dose level) and patients evaluable for efficacy analysis (efficacy dataset).

Enrolled Patients: This population will include all patients who are enrolled in the clinical study, regardless of whether patients receive treatment or not. This population will be evaluated in the analysis of patients' disposition.

Treated Patients: The treated patient population consists of all enrolled patients who actually receive at least one treatment administration. This population will be evaluated in the analysis of patient disposition, baseline characteristics, treatment exposure, efficacy and safety.

Patients evaluable for determination of DLT (by dose schedule and dose level): for each schedule and dose level tested, this population includes all patients enrolled in dose escalation part who receive at least 70% of drug in the first cycle, unless the reason for non-compliance is drug-related toxicity, and for whom a DLT assessment is available within the DLT window. In case the patient does not fulfill one or more of the aforementioned criteria, he/she will be replaced.

Patients evaluable for efficacy analysis (efficacy dataset): This is the patient population which consists of all enrolled patients in the Phase II part who are treated at the RP2D, have ≥ 1 on-treatment hematologic assessment(s) (i.e., they must have adequate bone marrow response evaluation). Patients who experience early death or withdrew prior to response assessment, or had technically suboptimal bone marrow sample precluding assessment, are non-evaluable for response and are excluded from the efficacy dataset. For cohort 1 and 2, only the subset of patients with FLT3-ITD mutation and no D835 mutation based on the central test will be included in this population.

For US only:

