Patients evaluable for efficacy analysis (efficacy dataset): efficacy datasets will be defined by dose level, patients receiving at least 75% of treatment at first cycle, have at least one or more on-treatment hematologic assessment(s) (i.e., they must have adequate bone marrow response evaluation), relative to ELN criteria, must have adequate baseline. Note: Patients who are not evaluable for efficacy due to early death, inadequate bone marrow sample, or withdrawal from the study prior to evaluation should be considered failures rather than non-evaluable

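### The Phase II efficacy dataset drops early deaths, early withdrawals and failed marrows; if it is the CRc denominator, as the visible text strongly suggests, the primary response rate is biased upward

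*Protocol*

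**What the plan says.** - **Endpoint.** SAP 3.2.1 gives the Phase II primary endpoint as "Composite Complete Remission Rate (CRc) = CR + CRi". Protocol 5.5 calls it a proportion of patients and names no analysis set. Each cohort has the same plan, for example "Cohort 1 (40 patients with a futility analysis at 10 patients").
- **Efficacy dataset.** Protocol 12.2 restricts it to Phase II patients treated at the RP2D with an adequate on-treatment marrow evaluation. It adds that "Patients who experience early death or withdrew prior to response assessment, or had technically suboptimal bone marrow sample precluding assessment, are non-evaluable for response". SAP 7 uses the same rule: such patients "are non-evaluable for response and are excluded from the efficacy dataset".
- **Treated patients.** Protocol 12.2 also assigns this wider set to "patient disposition, baseline characteristics, treatment exposure, efficacy and safety".
- **Futility.** Under Statistical Methods in the protocol Summary, each cohort is reviewed once at least 10 evaluable patients have been observed for at least 3 cycles. One CR or CRi lets the full cohort proceed. The Summary's CRc precision table, however, counts treated patients.
- **US paragraph of SAP 7.** This set is defined by dose level and limited to "patients receiving at least 75% of treatment at first cycle" who also have an adequate marrow response evaluation. It then says that patients with early death, an inadequate marrow sample or "withdrawal from the study prior to evaluation should be considered failures rather than non-evaluable".
- **Redactions.** The bodies of Protocol 12.3.4 and 12.4.1 and of SAP 9.7 and 5.2.1, where the CRc and futility denominators would be stated, are blacked out.

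**The concern.** Entry to the efficacy dataset depends on surviving, and staying on study, long enough to give a readable marrow. That is selection on a post-treatment outcome. Under the ELN 2022 criteria in Protocol Appendix 2.1, CR and CRi both require marrow blasts below 5%, so a patient with no adequate marrow cannot be classed as either. Each such exclusion shrinks the denominator and leaves the numerator unchanged, so the error runs in one direction only.

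CRc is the Phase II primary endpoint of a non-randomised study, so no concurrent arm shares and cancels the bias. A count of evaluable patients also decides whether a cohort continues past its futility look. The visible text leaves two candidate sets for efficacy. Protocol 12.2 says that it specifies the endpoints for each population, but it names none for the efficacy dataset.

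**Working it through.** **Step 1. Reproduce the plan's own figures.** Clopper-Pearson two-sided 95% limits for x responders in 10:

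| x | Plan | Recomputed |
|---|---|---|
| 1 | 0.25–44.50 | 0.25–44.50 |
| 2 | 2.52–55.61 | 2.52–55.61 |
| 3 | 6.67–65.25 | 6.67–65.25 |

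The half-widths agree within rounding (22.12 against 22.13, 26.54 against 26.55, 29.29 in both). The intervals are correct; the question is who enters the denominator.

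**Step 2. Inflation factor.** Take N treated patients who otherwise qualify, R responders and a non-evaluable share d. No excluded patient can be in R, so

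rate in evaluable = R / [N(1 − d)] = (R/N) × 1/(1 − d).

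The factor is 1/0.95 = 1.05 at d = 5%, 1/0.90 = 1.11 at 10%, 1/0.80 = 1.25 at 20% and 1/0.70 = 1.43 at 30%.

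**Step 3. Apply it to one cohort.** N = 40 is the planned cohort size. R = 8 and the values of d are assumptions.

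| d | Denominator | Rate | Exact 95% CI |
|---|---|---|---|
| 0 (all treated) | 40 | 20.0% | 9.1–35.6 |
| 5% | 38 | 21.1% | 9.6–37.3 |
| 10% | 36 | 22.2% | 10.1–39.2 |
| 20% | 32 | 25.0% | 11.5–43.4 |
| 30% | 28 | 28.6% | 13.2–48.7 |

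The relative effect does not depend on R. At d = 20%, 4 responders move from 10.0% to 12.5%, and 12 responders from 30.0% to 37.5%.

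**Step 4. Effect on futility.** A cohort passes with at least one responder in 10. If p is the rate among all treated, then P(pass) = 1 − (1 − p)^10 in 10 treated patients and 1 − [1 − p/(1 − d)]^10 in 10 evaluable patients.

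| p | 10 treated | 10 evaluable, d = 10% | d = 20% | d = 30% |
|---|---|---|---|---|
| 5% | 40.1% | 43.5% | 47.6% | 52.3% |
| 10% | 65.1% | 69.2% | 73.7% | 78.6% |

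For example, with p = 10% and d = 20%, p/(1 − d) = 12.5% and 1 − 0.875^10 = 73.7%.

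**Step 5. Is this set the CRc denominator?** Four visible facts point that way:
- it is named the efficacy dataset;
- it is limited to Phase II;
- the futility rule counts evaluable patients;
- SAP 9.2 speaks of patients excluded from the efficacy analysis.

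Two point the other way: Treated Patients is assigned to efficacy, and the precision table counts treated patients. The inference is strong but not stated.

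**Step 6. The US paragraph.** It requires an adequate marrow evaluation for entry, then counts patients without one as failures. Both conditions cannot govern the same patient.

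**The case against.** - **The denominator is not stated.** This is correct. The redacted sections may name the treated set as primary for CRc. In that case the inflation does not arise for the headline rate, though the futility count of evaluable patients would remain. The point is therefore conditional.
- **Phase II is exploratory and exclusions are disclosed.** SAP 9.1 reports patients excluded from the efficacy set with reasons, and the protocol lists all efficacy data by patient, so a reader could rebuild the all-treated rate. This lowers the severity. It does not make a post-treatment-selected set a sound basis for the primary rate or for a continuation decision.
- **A failed marrow is an unknown response, not an observed failure.** This is fair. For that subgroup, counting non-response is a conservative convention, and the inflation is measured against that convention.
- **Appendix 2.1 has a non-evaluable category.** It does, but it says nothing about denominators, so it supports neither side.

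A reader might infer two stronger points that the documents do not support. The first is that US and European patients have opposite denominators for the Phase II primary endpoint. SAP 3.2.2 says Phase II will not start in the US until a substantial amendment, and the US set is by dose level. It therefore currently concerns Phase I, and on the visible text no US patient enters the Phase II CRc estimate. The second is that an early death can never meet the US 75% condition. On Schedule A, 0.75 × 21 = 15.75, so the condition is met on day 16 of dosing; on Schedule B, 0.75 × 28 = 21, so on day 21. A patient who dies after that day and before an adequate marrow meets it. The real conflict in that paragraph is with the marrow requirement.

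**Conclusion.** The point holds in conditional form. The exclusion rule is explicit in both documents, and its direction is certain: it can only raise the CRc rate, by 1/(1 − d). The size rests on d, which the visible text does not give. At an assumed 10–30%, the relative inflation is 11–43%, or 2.2 to 8.6 percentage points on a true 20% all-treated rate. At a 10% all-treated rate, the chance of passing futility rises by 4.1 to 13.5 points over the same range.

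Two assumptions carry this: that the efficacy dataset is the CRc denominator, and that its definition of evaluable is the one used in the futility rule. The SAP's US rule, that the same three groups "should be considered failures rather than non-evaluable", shows that the sponsor already accepts the conservative convention elsewhere in this trial.

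**What to change.** 1. In Protocol 12.2 and SAP 7, name one primary CRc population: all treated Phase II patients assigned the RP2D who, on the central baseline test, are FLT3-ITD positive and negative for D835 and I836. SAP 7 names only D835 and should be aligned with the protocol. The mutation restriction rests on a study-entry test, so it does not raise the same problem.
2. Count patients without an adequate on-treatment marrow as non-responders.
3. Use the same denominator for the futility count, and make the precision table and the futility rule use the same term.
4. Keep the evaluable set as a labelled supportive analysis.
5. In the US paragraph of SAP 7, remove the adequate-marrow entry requirement that conflicts with its failure rule.

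The cost is wording in the protocol and SAP, with no new visits, data or patients. The reported CRc rate will be somewhat lower, and technically failed marrows will count as non-response even where the true status is unknown. The supportive analysis shows how much that matters.
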